APPENDIX 1: METABOLIC SYNDROME CRITERIA

Metabolic syndrome in this study will be defined as having at least 3 of the identified risk factors (Alberti et al., 2009).

Table 1. Criteria for Clinical Diagnosis of the Metabolic Syndrome

Measure	Categorical Cut Points
Elevated waist circumference*	Population- and country-specific definitions
Elevated triglycerides (drug treatment for elevated triglycerides is an alternate indicator†)	≥150 mg/dL (1.7 mmol/L)
Reduced HDL-C (drug treatment for reduced HDL-C is an alternate indicator†)	<40 mg/dL (1.0 mmol/L) in males; <50 mg/dL (1.3 mmol/L) in females
Elevated blood pressure (antihypertensive drug treatment in a patient with a history of hypertension is an alternate indicator)	Systolic ≥130 and/or diastolic ≥85 mm Hg
Elevated fasting glucose‡ (drug treatment of elevated glucose is an alternate indicator)	≥100 mg/dL

HDL-C indicates high-density lipoprotein cholesterol.

*It is recommended that the IDF cut points be used for non-Europeans and either the IDF or AHA/NHLBI cut points used for people of European origin until more data are available.

†The most commonly used drugs for elevated triglycerides and reduced HDL-C are fibrates and nicotinic acid. A patient taking 1 of these drugs can be presumed to have high triglycerides and low HDL-C. High-dose ω -3 fatty acids presumes high triglycerides.

\$\pmox{Most patients with type 2 diabetes mellitus will have the metabolic syndrome by the proposed criteria.

APPENDIX 2: ELEVATED ALT OR WORSENING HEPATIC FUNCTION STUDY MODIFICATION AND PATIENT DISCONTINUATION RULES

Treatment-Emergent ALT	Treatment-Emergent Total Bilirubin (TBL)	Liver Symptoms	Action	
Normal baseline: ALT >5× ULN	Normal	None	Repeat ALT, AST, ALP, TBL, in 2–3 days	
Elevated baseline: ALT >3× baseline or >300 U/L			Follow-up for symptoms.	
(whichever occurs first)				
Normal baseline: ALT >8× ULN	Normal	None	Interrupt study drug. Initiate close observation and workup for competing etiologies. (see below)	
Elevated baseline: ALT >5× baseline or >500 U/L				
(whichever occurs first)			Study drug can be restarted only if an alternative etiology is identified and liver enzymes return to baseline.	
Normal baseline: ALT >3× ULN	TBL >2× ULN	None	Interrupt study drug. Initiate close observation and workup for competing etiologies.	
Elevated baseline: ALT >2× baseline or >200 U/L			Study drug can be restarted	

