(whichever occurs first)			only if an alternative etiology is identified and liver enzymes return to baseline.	
Normal baseline: ALT >3× ULN	Normal or elevated	Symptoms of clinical hepatitis - severe fatigue, nausea, vomiting,	Interrupt study drug. Initiate close observation and workup for competing etiologies.	
Elevated baseline: ALT >2× baseline or >200 U/L			Study drug should not be	
(whichever occurs first)		right upper quadrant pain	restarted	

ALP=alkaline phosphatase; ALT= alanine aminotransferase; AST= aspartate aminotransferase; TBL=total bilirubin. Source: Adapted from Chalasani, Naga and Regev, Arie et al. Drug-Induced Liver Injury in Subjects with Preexisting Chronic Liver Disease in Drug Development: How to Identify and Manage? Gastroenterology, Volume 151, Issue 6, 1046 – 1051

Close observation for potential drug-induced liver injury (DILI):

Within 72 hours, perform a complete history, physical, and liver biochemistries, including evaluation of:

- New or worsening signs and symptoms of clinical hepatitis such as fatigue, nausea, vomiting, right upper quadrant pain or tenderness, fever, rash, or eosinophilia
- Concomitant medications, including acetaminophen, dietary supplements, herbal remedies, over-the-counter medications, recreational drug use, and special diets
- Alcohol consumption
- Exposure to environmental chemical agents
- Past medical history
- Complete review of systems
- Liver biochemistries including alanine aminotransferase (ALT), aspartate aminotransferase (AST), alkaline phosphatase (ALP), gamma-glutamyl transferase (GGT), total bilirubin, direct bilirubin, and international normalized ratio (INR)
- Ruling out acute viral hepatitis type A, B C D and E; autoimmune or alcoholic hepatitis; nonalcoholic steatohepatitis (NASH); hypoxic/ischemic hepatopathy; and biliary tract disease (abdominal ultrasound).
- Consider gastroenterology or hepatology consultations

Evaluate patients 2 or 3 times a week for signs and symptoms of clinical hepatitis and obtain liver biochemistries until biochemistries stabilize or the trial drug has been discontinued and the patient is asymptomatic. If biochemistries stabilize and the patient is asymptomatic, monitor liver biochemistries once a week until they return to baseline. Analysis of such biochemistries may occur at local lab.

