If the baseline liver enzymes are normal, follow the FDA guidance on "Drug- Induced Liver Injury: Premarketing Clinical Evaluation" for monitoring and managing patients if the patients experience elevations in liver enzymes during the clinical trial.

Patients who live far from study sites may be evaluated locally for history, physical exam, and laboratories, if the results are communicated promptly to the site Investigator.

Additional laboratory criteria to detect DILI:

• Interrupt the treatment and initiate DILI evaluation if:

- O Alkaline phosphatase (ALP)>2x ULN and direct bilirubin (DB) >2x ULN, if ALP and DB are normal at baseline
- \circ ALP >2x baseline and DB >2x baseline if they are elevated at baseline
- ALP >2x baseline and DB >2x baseline and symptoms consistent with clinical hepatitis
- In the event of liver enzyme elevation, perform a DILI evaluation. If a clear etiology is established to account for the liver enzyme abnormalities, and the liver enzymes return back to baseline, the study drug may be restarted.
- If upon rechallenge, any magnitude of liver enzyme elevation recurs, the patient should cease the treatment drug and should be followed in the study. If a patient cannot be followed with laboratory or clinical monitoring, rechallenge should not be performed.

Stopping rule for progression to cirrhosis during the study:

APRI (using 40 U/L as ULN) will be calculated per SOA at baseline, Day 113 (Week 16), then every other dosing day (approximately every 168 days) or earlier if development of cirrhosis is suspected clinically, which may include development of varices, decompensating events or new thrombocytopenia and splenomegaly. Any increase from baseline to an APRI value >2.0 (must be confirmed on repeat) will trigger liver biopsy. For patients with baseline APRI >2.0 but who are eligible based on pre-dose biopsy, APRI will be calculated per SOA and a \geq 50% increase from baseline (must be confirmed on repeat) will trigger liver biopsy.

Investigator may elect to confirm an elevated APRI as a biomarker of cirrhosis with MRE if available PRIOR to proceeding to biopsy. If MRE is NOT consistent with cirrhosis then biopsy is not indicated and the patient may stay on study. Alternatively, the Investigator may elect to proceed directly from APRI to biopsy.

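### Appendix 2 does not say which of two restart rules governs after a symptomatic ALT rise, and its ALP/direct bilirubin interruption trigger, read literally, omits asymptomatic patients with one marker raised at baseline

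*Protocol*

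**What the plan says.** The table in Protocol Appendix 2 has four rows. Rows 2, 3 and 4 interrupt study drug.

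- **Rows 2 and 3** (no symptoms) allow a conditional return: "Study drug can be restarted only if an alternative etiology is identified and liver enzymes return to baseline".
- **Row 4** applies to an ALT rise accompanied by "Symptoms of clinical hepatitis - severe fatigue, nausea, vomiting" or right upper quadrant pain, with bilirubin normal or raised. Its action is that "Study drug should not be" restarted. No condition lifts this.

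Below the table, under the additional laboratory criteria for DILI, are two further rules.

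- **ALP/DB trigger.** Treatment is interrupted and a DILI evaluation started under any of three limbs. Limb 1 is both markers above twice the upper limit of normal (ULN), "if ALP and DB are normal at baseline". Limb 2 is "ALP >2x baseline and DB >2x baseline if they are elevated at baseline". Limb 3 is "ALP >2x baseline and DB >2x baseline and symptoms consistent with clinical hepatitis".
- **Restart bullet.** It opens "In the event of liver enzyme elevation, perform a DILI evaluation" and goes on to say that if a definite cause accounts for the abnormality and "the liver enzymes return back to baseline, the study drug may be restarted".

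Section 6.3 and the synopsis stopping rules refer to Appendix 2 for hepatic events and do not rank its parts.

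**The concern.** **Restart.** ALT is a liver enzyme, so a row 4 event falls within the wording of the bullet. The bullet does not except row 4 and does not mention symptoms. A site holding a recovered patient with an identified cause has one text that forbids re-dosing and another that allows it.

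**ALP/DB trigger.** Limb 1 is conditioned on both markers being normal at baseline, limb 2 on both being raised, and limb 3 on symptoms. A patient who starts with one marker raised and one normal, and has no symptoms, meets none of these conditions however far both markers rise. Such a patient can be enrolled: the numbered exclusions in Section 7.3 limit INR, platelets, ALT/AST and eGFR but set no limit for ALP or bilirubin, and only investigator judgement would apply.

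At stake is whether a patient with symptomatic liver injury is re-dosed, and whether a cholestatic rise explicitly stops dosing. Patients with fibrosis may receive up to 18 doses, so these rules stay in use for a long time.

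**Working it through.** The plan gives no figure to reproduce. The check is a comparison of texts and a count of logical cases.

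**1. Restart after a row 4 event.** The bullet has two conditions, cause found and enzymes back to baseline, which gives 2 × 2 = 4 outcomes.

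| Cause found | Enzymes recovered | Row 4 | Bullet |
|---|---|---|---|
| no | no | no restart | no permission given |
| no | yes | no restart | no permission given |
| yes | no | no restart | no permission given |
| yes | yes | no restart | restart allowed |

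The texts diverge in 1 of the 4. Among the three rows that interrupt drug, only row 4 is affected, because the bullet's conditions match those of rows 2 and 3.

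**2. ALP/DB trigger.** Cross baseline ALP (normal or raised), baseline DB (normal or raised) and symptoms (no or yes): 2 × 2 × 2 = 8 combinations. Suppose that on treatment both markers exceed both 2× ULN and 2× baseline.

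| Baseline ALP | Baseline DB | No symptoms | Symptoms |
|---|---|---|---|
| normal | normal | limb 1 | limbs 1, 3 |
| raised | raised | limb 2 | limbs 2, 3 |
| raised | normal | none | limb 3 |
| normal | raised | none | limb 3 |

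A limb is met in 6 of 8. The two unmet cells are the asymptomatic mixed baselines.

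*Illustration (assumed values).* Baseline ALP 1.5× ULN and DB 0.8× ULN; on treatment ALP 5× ULN and DB 6× ULN; no symptoms. ALP has risen 5/1.5 = 3.3-fold and DB 6/0.8 = 7.5-fold. Limb 1 fails because ALP was not normal at baseline, limb 2 because DB was not raised, and limb 3 because there are no symptoms. Judged marker by marker, both qualify: ALP is above 2× its raised baseline, and DB is above 2× ULN from a normal baseline.

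**3. What else in Appendix 2 catches these patients?**

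- *Restart bullet.* Its first sentence requires a DILI evaluation for liver enzyme elevation, with no threshold and no baseline or symptom condition. ALP is a liver enzyme, so work-up is covered. The sentence does not order interruption.
- *ALT table.* Without symptoms and with raised total bilirubin, row 3 is the relevant row. It needs total bilirubin >2× ULN and ALT >3× ULN (normal baseline), or >2× baseline or >200 U/L (elevated baseline). Take an assumed ALT ULN of 40 U/L and total bilirubin of 3× ULN. ALT going from 30 to 100 U/L stays below 3 × 40 = 120. ALT going from 60 to 110 U/L stays below 2 × 60 = 120 and below 200. Neither case meets row 3, so a mainly cholestatic rise can miss the table.
- *FDA-guidance sentence.* It applies where baseline liver enzymes are normal. Split the two unmet cells by whether all other baseline enzymes are normal: 4 sub-cases. Counting ALP as an enzyme and DB as not one, the sentence can apply in 1 (ALP normal, DB raised, other enzymes normal). The protocol states no threshold from that guidance.

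**The case against.** **On restart.** A specific bar and a general permission need not contradict each other. The bullet obliges nobody to re-dose, and withholding drug satisfies both texts. It sits under a heading for additional criteria, so it supplements the table. Reading it to override row 4 would erase the evident difference between row 4 and rows 2 and 3. This is persuasive about intent. It does not supply the missing precedence, because the bullet speaks of liver enzymes generally and is not confined to ALP and DB.

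**On the trigger.** The pronoun in limb 2 can be read marker by marker, each compared with its own reference, and that closes the gap. This is clinically natural and may well be what was meant, but it is not what limbs 1 and 2 literally state.

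**On consequences.** Section 6.3 frames these events as ones that may lead to stopping. It involves the DSMB in individual decisions and lets the sponsor or investigator discontinue a patient at any time. After Week 16, doses are 12 weeks apart with pre-dose laboratory tests, which normally leaves time for review. Any enzyme rise after rechallenge stops treatment. All of this reduces the harm. None of it says which restart rule governs, and the rechallenge rule acts only after re-dosing.

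**Readings to avoid.** A reader might infer that the protocol directs re-dosing after symptomatic hepatitis; the bullet only permits it, and row 4 forbids it. A reader might also infer that mixed-baseline patients go undetected; the DILI evaluation requirement rules that out wherever an enzyme rises.

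**Conclusion.** Both points hold as minor patient-safety wording defects.

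- **Restart:** precedence is unstated in 1 of 4 row 4 outcomes. The row 4 bar is the safer and probably intended reading.
- **ALP/DB trigger:** on a literal reading, 2 of 8 combinations have no limb. What is missing there is only the explicit instruction to interrupt drug; evaluation is already required for an enzyme rise, and some of these patients will also meet an ALT row.

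These are counts of logical cases, not frequencies. The documents do not show how many of the approximately 36 patients have a mixed baseline or might have a row 4 event. The second point rests on reading limbs 1 and 2 as each referring to both markers. How far the cited FDA guidance would fill either point cannot be judged from the documents. Nothing here bears on the Week 16 primary analysis, the sample size or the power.

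**What to change.** 1. Add to the restart bullet: *except where the table above states that study drug should not be restarted*.
2. Replace limbs 1 and 2 with one rule applied to each marker: above 2× ULN if that marker was normal at baseline, above 2× its own baseline if it was raised, with both markers required. Keep the symptomatic limb. All 8 combinations then have a limb, and the both-normal and both-raised cases are unchanged.

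The cost is two wording changes and a notice to sites. Because they touch patient safety, Section 12.2 would require ethics committee approval. No visits, procedures, samples or analyses are added.

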APPENDIX 3: PULMONARY FUNCTION MONITORING

Pulmonary function will be monitored closely throughout the AROAAT2001 study using spirometry, DLCO, periodic DSMB reviews, weekly Sponsor reviews and medical monitoring for pulmonary AEs.

If a patient in the AROAAT2001 study experiences an absolute decline of 10% or more in percent of predicted FEV₁ (must be confirmed on repeat within 30 days) from baseline with symptoms of chronic obstructive pulmonary disease (COPD) exacerbation,

OR experiences an absolute decline in percent of predicted FEV₁ by 10% (must be confirmed on repeat within 30 days) AND a decline in percent of predicted DLCO of at least 10%,

OR an absolute decline of percent of predicted FEV₁ of 20% or more (must be confirmed on repeat within 30 days), regardless of concurrent symptoms and regardless of any drop in percent of predicted DLCO,

they will be referred to a pulmonologist for possible initiation of augmentation therapy. Arrowhead will provide the therapy in any instance where the patient cannot access it through normal channels. Additionally, pulmonary monitoring visits for spirometry will be increased to approximately monthly.

If deemed necessary by the treating pulmonologist, AAT augmentation therapy may be initiated per locally approved package insert (typically weekly infusions at 60 mg/kg per dose) or equivalent for the duration of the AROAAT2001 study while the patient is on fazirsiran (or placebo) and for up to an additional 6 months after the patient's serum Z-AAT levels have returned to within 30% of their pre-dose Day 1 baseline serum AAT value OR until AAT levels have returned to within 30% of pre-dose Day 1 baseline and pulmonary function parameters (either DLCO or FEV1) have stabilized (defined as 2 sequential measurements that are not declining) OR until cessation of augmentation therapy is deemed appropriate by treating pulmonologist. In the circumstance of patients in the study newly started on AAT augmentation therapy, measurement of serum AAT may increase in frequency from SOA to monthly or every 2 weeks. This measurement may be done with a Z-AAT specific assay or may require occasional AAT augmentation washout for measurement of endogenous production using the clinical AAT assay. In countries where augmentation is not available or not reimbursed, the Sponsor will work to make therapy available as part of the AROAAT2001 clinical study.

Each patient newly started on augmentation therapy during the study due to declines in FEV₁ and/or DLCO as described above will be reviewed by the DSMB to assess if the patient should continue to receive treatment with fazirsiran or placebo. Additionally, the DSMB will evaluate for imbalances in adverse changes in FEV₁, DLCO and pulmonary AEs in active versus placebo groups at each planned DSMB meeting.

APPENDIX 4: BIRTH CONTROL METHODS CONSIDERED HIGHLY EFFECTIVE

Methods that can achieve a failure rate of less than 1% per year when used consistently and correctly are considered as highly effective birth control methods. Such methods include:

combined (estrogen and progestogen containing) hormonal contraception associated with inhibition of ovulation:
oral
intravaginal
transdermal
progestogen-only hormonal contraception associated with inhibition of ovulation:
oral
injectable
implantable
intrauterine device (IUD)
intrauterine hormone-releasing system (IUS)
bilateral tubal occlusion
vasectomized partner
sexual abstinence, defined as refraining from heterosexual intercourse only when this method is in alignment with the normal lifestyle of the patient
Birth control methods that result in a failure rate of more than 1% per year when used alone or in combination, thus are NOT considered highly effective include:
progestogen-only oral hormonal contraception, where inhibition of ovulation is not the primary mode of action
male or female condom with or without spermicide
cap, diaphragm, or sponge with spermicide

APPENDIX 5: DISCUSSION OF RISKS ASSOCIATED WITH STUDY ASSESSMENTS

Many of the assessments in the study i.e., liver biopsy, noninvasive hepatic imaging (FibroScan®), magnetic resonance imaging (MRI)/magnetic resonance elastography (MRE) and laboratory measurements are often part of a standard evaluation for liver disease severity made by a consulting physician treating a patient with AATD liver disease. Risk Assessments for patients are described in Section 4.8 of the study protocol. Assessments such as pulmonary function tests (PFTs), FibroScan® and MRE are noninvasive and involve minimal risk. Liver biopsy is an invasive assessment but is of critical importance in this study. AROAAT2001 is an innovative clinical study that requires liver biopsy to assess the novel histological primary endpoint and rating scale. Further assessment of the risk/benefit of the study assessments are summarized below:

- PFTs as used in the study (spirometry and DLCO) are standardly used to evaluate lung function in alpha-1 patients. A key benefit of this assessment is to track lung function during the study to evaluate for lung toxicity. There is very minimal risk associated with pulmonary function testing.
- FibroScan® and Magnetic Resonance Elastography (MRE) are noninvasive imaging modalities commonly used to evaluate liver disease in AATD and are of minimal risk for patients. The key clinical research benefit of these noninvasive imaging procedures is to track changes in liver stiffness related which in this study is being explored as markers for liver fibrosis and liver disease severity in patients with AATD-associated liver disease.
- Liver biopsy is the most invasive assessment in the study. Performance of liver biopsies is commonly part of the standard of care in patients with liver disease related to AATD as well as other adult liver diseases. While it is a common procedure, like any procedure it is associated with some risk. The risk of bleeding associated with biopsies requiring blood transfusion or hospitalization is 0.04% or less and the risk of less severe but clinically significant events (causing pain, tachycardia, or lower BP) is estimated at 0.2% (Rockey et al., 2009). Several larger studies show that complications and serious bleeding related to liver biopsy are overwhelmingly more likely in patients with serious clotting disorders, malignancy, and other serious health conditions that are described in the exclusion criteria for this study. The following risk mitigations are implemented in the protocol:
 - Liver biopsies are being performed by experienced physicians with appropriate local procedural credentials, in the setting of a hospital facility experienced with such procedures.

[figure not shown]
Measures of hemostatic function (e.g., platelets, international normalized ratio [INR]) will be conducted prior to biopsy, and may be used to exclude any patient at increased risk for procedural complications.

Thrombocytopenia and elevated INR are exclusionary for this study. Therefore, the risk of liver biopsy related complications in this study is acceptable and similar to other studies using liver histology as an endpoint.

Monitoring and recovery of the patient following the procedure will be consistent with locally accepted standards of clinical practice. Liver biopsy is the only method for obtaining the tissue specimens needed to evaluate the primary endpoint of the study.

Demonstration of an intrahepatic reduction of the disease-causing Z-AAT protein in response to fazirsiran is the pharmacologic and efficacy assessment which is most clinically relevant to patients with AATD-associated liver disease. Thus, the minimal risk of liver biopsy is justified in light of its use to obtain tissue samples required to assess clinically meaningful changes in intrahepatic Z-AAT protein and histology as represented by multiple key secondary study endpoints.

Signature Page for VV-CLIN-000130 v2.0

Signature Page for VV-CLIN-000130 v2.0

HCV	Hepatitis C virus
HIV	Human Immunodeficiency Virus
ICH	International Conference on Harmonisation
IRB	Institutional Review Board
ISR	Injection Site Reaction
LD	Lactate Dehydrogenase
LISR	Local Injection Site Reaction
MCH	Mean Cell Hemoglobin
MCHC	Mean Cell Hemoglobin Concentration
MCV	Mean Cell Volume
mmHg	millimeters of mercury
MRE	Magnetic Resonance Elastography
MRI	Magnetic Resonance Imaging
MRI-PDFF	Magnetic Resonance Imaging Proton Density Fat Fraction
PD	Pharmacodynamic
РВО	Placebo
PI	Principal Investigator
PiZZ	Homozygous Z allele individuals
РК	Pharmacokinetic
РТ	Prothrombin Time
PTT	Partial thromboplastin time

Abbreviation	Definition
RNAi	RNA interference
SAE	Serious Adverse Event
SD	Standard Deviation
siRNA	Short interfering RNA oligonucleotides
SOA	Schedule of Assessments
TIA	Transient Ischemic Attack
ULN	Upper Limit of Normal
Z-AAT	Mutant AAT protein from Z allele

